5.4 Blinding, Packaging, and Labeling

The vials with lyophilized azithromycin will be stored at room temperature (30 °C or 86 °F) or below, under lock, pending preparation by the study site hospital pharmacist, according to study allocation schedule and detailed procedures described in Appendix C procedures for dilution in 2 steps. The investigator will provide the pharmacist in a timely fashion with a precise schedule for treatment days for a given subject (initials and code #) to be treated. Dilution of active drug will be performed with sterile saline 0.9 % purchased at study start by hospital pharmacy (same batch). Placebo will be prepared with the same sterile saline solution. The infusion pouches will be delivered to the investigator at regular intervals during the period as considered most convenient for pharmacy and clinical site (daily, 1, 2 or 3 times a week), providing storage temperature is respected (room temperature up to 24 hours, 5 °C or 41 °F up to 7 days until 1 hour prior to administration). The code will not be discussed or alluded to by the pharmacist, either when discussing with the investigator and his staff, the patient or the monitor to maintain the double blind conditions.

The twin study labels (multilingual as required) for the clinical supplies will be printed for each subject and each study day by Quintiles, the left side label being attached to the infusion pouch by the pharmacist, and the right side label being later detached and affixed to the CRF. The expiry date provided on the labels of both study drugs (azithromycin, saline) will correspond to the date of administration (7 days if pouch stored at 5°C, 1 day if stored at room temperature) and not to the azithromycin batch expiry date. These labels will contain the following information:

Study labels for distribution to investigator

To be attached on pouch

To be attached on CRF

ANB 006 #2001	
Azithromycin or Placebo for i.v. infusion	
Store 5 °C or 41 °F, do not freeze, 250 mL	
Drug exclusively for clinical trial	
Regulatory text (country specific)	
Allocation #	Anbics
Day 1, 2, 3,.....	Zurich
Expiry date.....	Batch.....

ANB 006 #2001	
Allocation #	
Day 1, 2, 3,...	
Date dispensed.....	
Anbics	
Zurich	
Batch.....	

5.5 Supplies and Accountability

The site pharmacist will inventory and acknowledge receipt of all shipments of study medication which must be kept at room temperature or below, pending preparation and dilution as stated above under Section 5.4. and in Appendix C.

All study medication must be kept in a locked area with access restricted to designated study personnel. The investigator and pharmacist will also keep accurate records of the quantities of study medication prepared and dispensed. During the study the monitor will inquire at regular intervals (such as every 4 patient block) on number of available azithromycin vials. The site monitor will check the supplies of study medication held and dispensed by the pharmacist and administered by the investigator to ensure accountability of all study medication used, but only after study completion, after the database has been frozen, and the code has been unblinded. At the conclusion of the study, all unused study medication and all medication containers will be destroyed locally under appropriate control and documentation unless other arrangements have been approved with the sponsor's representatives. A final report of drug accountability as agreed with the site monitor will be prepared and maintained by the pharmacist.

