4.3 Exclusion Criteria

Subjects presenting with any of the following will not be included in the study:

- Poor prognosis as judged by Apache II score >25
- Pregnant females
- Grossly under- or overweight (BMI <18 or >29)
- Ongoing therapy with a macrolide (clarithromycin, erythromycin, azithromycin, telithromycin)
- Known allergy to any macrolides
- Proven *P. aeruginosa* pneumonia (with documented CFU>10⁴ in BAL or PBS)
- Ongoing antipseudomonal therapy with a susceptible colonizing strain as proven by antibiogramme*

* A list of recommended antibiotics deprived of antipseudomonal activity is provided in Section 6.2 to facilitate the choice of the investigators and to homogenize antibiotic treatment according to type of infections. For patients on antibiotherapy with activity against pseudomonas prior to study entry, they will be maintained in the screening phase for 48 hrs, pending results of antibiogramme on the colonized strain. If found to be susceptible to the antibiotic used, the patient will be excluded from the study; if found to be resistant, the patient will be included in the study (also see Section 6.2)

- Anticipated short duration of mechanical ventilation (≤ 3 days)
- Known drug interaction which could interfere enough with absorption, metabolism, or excretion and thus could decrease efficacy or raise safety concern despite plasma drug monitoring of concomitant therapy (for examples see Section 6.2)
- Severe hepatic insufficiency (type C i.e. score >10 on Child Pugh scale, Appendix A) [Pugh et al 1973]
- Sick sinus syndrome or known long QT syndrome or $QTc >500$ msec
- Recent donation of blood or participation in another clinical trial within 3 months (Europe) or 1 month (USA)
- Any situation exposing the patient to higher risk or possibly confounding results of the study

Any local or country specific regulations must be respected. Any waiver of the inclusion and exclusion criteria listed above must be approved by the investigator and by the monitor on a case-by-case basis prior to enrolling the subject. This must be documented by both the monitor and the investigator.

No subject will be allowed to enroll in this study more than once if study drug was administered. However a patient may be screened on a 2nd occasion under another screening number if he did not meet all inclusion and exclusion criteria in the first instance.

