5.2 Dosage Schedule

At each study site, the study medication will be prepared by the hospital pharmacist, using the method described in Appendix C, the randomization numbers allocated to the site and the randomization code provided by the independent statistician. The pouches will be infused i.v. by the investigator or his delegate, carefully following the procedures set out in this study protocol. Administration of study drug will be time zero, Day 1 (i.e. t=0 start of infusion) and the i.v. infusion will last 1 hour. Exact date, start

and completion time of infusion will be recorded daily in the case report form (CRF). If a central line is available, the study drug will be preferably infused by that port, avoiding any other concomitant infusion.

Efforts will be made to comply with a 24 hour interval between daily doses for a given patient throughout the treatment period as much as technically feasible. The maximum duration of treatment will be 20 days.

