5.3 Treatment Assignment

The study medication will be administered only to subjects included in this study following the procedures set out in the study protocol.

Since the screening period is expected to be short, no dedicated **subject numbers** will be allocated in advance but only a simplified code combining centre number (1, 2, 3, ...), letter S (for screening), and the chronological number of entry (1,2,3,...). Thus, in Centre 5, the 11th patient screened would have the subject number **5-S11**, and, in Centre 12, the 2nd patient screened would carry the subject number **12-S2**. This subject number will be used to identify the subject between initiation and completion of screening, with verification of inclusion/exclusion criteria, and on Day -1. Thereafter, starting on Day 1, each subject will be assigned a **randomization number**, both sequentially and in chronological order, which will combine the study site number and a study medication number i.e. #05108 for centre 5 and 8th patient. Each patient will receive the corresponding study medication (placebo or azithromycin), labeled with that same code number. The investigator will record in the CRF the subject screening number and the 5-digit randomization number.

The study medication will be randomly assigned in advance to the randomization numbers taken into consideration the study site (#01101 to 01124 for centre 1) for a maximum of 25 study sites although 20 sites are targeted initially, according to the randomization plan generated by the Biometrics Department of Quintiles for each site and following a balanced basis (equal groups), by blocks of 4. Each centre will have a different allocation schedule. Each centre will initially receive the number of azithromycin vials corresponding to treatment for 25% of committed patients assuming 20 days of treatment (2 boxes of 10 vials per patient) and taking into account the anticipated patient recruitment (8, 12, 16, 20,...) Additional vials will be shipped to each centre based on recruitment and duration of treatment. Supplementary azithromycin vials will be maintained at disposal of centers recruiting beyond original plans or for new centres in case of need. The randomization plans will be stored with the Biometrics Department. Subjects withdrawn from the study will retain their subject number and their randomization number if drug has already been administered. New subjects must always be allotted a new subject number.

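### Section 5.5 has the site monitor ask for azithromycin vial stock during the study, which can partly or fully decode a block of 4 although the monitor is meant to stay blind

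*Protocol*

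**What the plan says.** Two provisions keep the monitor blind. Section 5.4 states that "The code will not be discussed or alluded to by the pharmacist" and names the monitor among those with whom this silence must be kept. Section 5.5 postpones the monitor's check of supplies until the database is frozen and the code is broken.

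Section 5.5 nevertheless provides, while the study runs, that "the monitor will inquire at regular intervals (such as every 4 patient block) on number of available azithromycin vials".

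The rest of the protocol gives that number its meaning:
- Section 5.3: allocation is "following a balanced basis (equal groups), by blocks of 4"; "Each centre will have a different allocation schedule"; and "each subject will be assigned a randomization number, both sequentially and in chronological order". A patient's block can be read from the randomization number.
- Section 5.3: supply is planned "assuming 20 days of treatment (2 boxes of 10 vials per patient".
- Appendix C: an active pouch takes 3.0 mL from a reconstituted vial; a placebo pouch is plain saline with no dummy vial.
- Section 5.2: the date, start and "completion time of infusion will be recorded daily in the case report form (CRF".
- Section 14.1: the site monitor checks the CRF against source documents in full.

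No unblinded supply monitor, dummy vial or varying block size is described.

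**The concern.** Only patients on azithromycin consume vials. Someone who knows how many vials a block used, and how many days each of its four patients was infused, can ask which two patients' days account for the total. There are only six balanced allocations, so the answer is often unique, and even when it is not, it may settle one patient's arm. The enquiry thus releases early much of what the postponed accountability check is there to withhold.

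The monitor verifies the CRF and source data, is in frequent contact with sites (13.1), and co-approves eligibility waivers, which "must be approved by the investigator and by the monitor on a case-by-case basis" (4.3). The expert panel works from the CPIS parameters, symptoms, X-rays and cultures supplied to it (7.2.4), so knowledge of the arm could colour the queries raised on those data.

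The primary comparison rests on about 10 cases. With an assumed 75 patients per arm, Fisher's two-sided test gives p = 0.098 for 8 versus 2 cases and p = 0.166 for 7 versus 2, so one case can move the result across the stated 0.10 level. That shows how sensitive the result is; it does not show that such a shift is likely.

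**Working it through.** **Vials per active day.** 3.0 mL x 100 mg/mL = 300 mg, which one 500 mg vial covers. One vial x 20 days = 20 vials = 2 boxes of 10, the supply figure in 5.3. Placebo uses 0.

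**Decoding rule.** If the four patients of a block have d1 to d4 treatment days and each pouch is made on the day, vials used = the sum of d over the two active patients. The number of allocations is C(4,2) = 6. Without a count, a guess at the block is right with probability 1/6 = 16.7%, and no patient is known with certainty.

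**Illustration.** Take days 4, 7, 11 and 20. The six pair totals are 4+7 = 11, 4+11 = 15, 4+20 = 24, 7+11 = 18, 7+20 = 27 and 11+20 = 31. All differ, so any total identifies all four arms. With pouches prepared in sixes and no more than 20 per patient, the vials per patient become 6, 12, 12 and 20, and the totals 18, 18, 26, 24, 32 and 32. A count of 18 now fits two allocations, but both have the 4-day patient on active drug and the 20-day patient on placebo.

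**How often.** For simulated blocks, count how many of the six allocations fit the observed total. The durations are assumptions. The base set is four distributions: uniform 3-20 days, and exponential with mean 7, 10 or 14 days capped at 20.

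| Setting | All four arms fixed | At least one arm known |
|---|---|---|
| Exact count, daily preparation (base set) | 67-77% | 96-97% |
| 3-pouch batches, batching known (base set) | 37-47% | 76-93% over both batch sizes |
| 6-pouch batches, batching known (base set) | 17-29% | as above |
| Unknown waste, 0-2 pouches per active patient (base set) | 25-32% | 51-84% over both waste ranges |
| Unknown waste, 0-5 pouches per active patient (base set) | 9-14% | as above |
| Exact count, days uniform 5-9 | 35% | 86% |
| Exact count, half reach Day 20 | 39% | 92% |
| Exact count, 75% reach Day 20 | 11% | 67% |

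With days uniform on 1-20, exact enumeration gives 78.6% of blocks fully fixed. An unknown count error of up to 1, 2 or 3 vials lowers this to 49%, 31% and 22%, with at least one arm known in 89%, 81% and 72%. If only a two-block total is known, full decoding falls to 29%. In the harshest combination tried (days uniform 5-9, unknown error up to 3 vials), 5% of blocks are fully fixed and at least one arm is known in 24%.

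**Overlap of blocks.** 240 patients / 20 sites = 12 per site over about a year, each treated for at most 20 days, so overlap within a site should be limited.

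**The case against.** The strongest objection is that vials are consumed by pouches prepared, not by pouches infused. Appendix C lets the pharmacist hand over 1, 3 or 6 pouches at a time, and treatment can end without notice through extubation, pneumonia or death. Pouches made up and never used break the match with CRF days. This stands, and it lowers full decoding from 67-77% to 17-47% or less.

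Second, 5.5 speaks of vials available, not vials used, and gives the block only as an example interval. The monitor would also need the shipments and a moment when one block has finished and the next has not begun. This stands too. The text permits the leak without guaranteeing a clean count for each block.

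Third, a reader might infer that waiver decisions and the work-up of suspected pneumonia would be biased. For a count taken after a completed block the documents do not support that: the next block is randomized afresh, and the final treatment days needed for decoding are known only after the Day x work-up. Those routes open only if a count is taken mid-block, which regular intervals allow; a count with a single patient on treatment would show that patient's arm.

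Fourth, the monitor assesses no endpoint. Pneumonia rests on culture thresholds and CPIS and is confirmed by a separate blinded panel (7.2.4, 11.4), and laboratory parameters are assessed blind (7.3). Any effect on the primary result is therefore indirect and cannot be quantified from the protocol.

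None of this explains why a monitor who is meant to be blind should receive the count.

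**Conclusion.** The contradiction is in the protocol's own text: 5.4 and part of 5.5 keep the site monitor blind, while another sentence of 5.5 gives the monitor a number from which allocation can be partly or fully worked out.

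It would be too strong to say that the enquiry usually reveals who is on active drug or defeats the blind. That holds for full identification only with near-exact counts, daily preparation and widely varying durations, none of which the protocol fixes. It fails when pouches are batched, waste is unknown, durations cluster, or half or more of the patients reach Day 20. Partial leakage is more robust: at least one arm is known in about half to 97% of blocks across the tabulated settings, and in fewer only when narrow durations and count errors combine.

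The consequence is an indirect risk of bias through retrospective queries and site contact. The point should be corrected because the rule breaks the plan's own blind and is cheap to remove. Confidence is moderate, since every percentage depends on assumed durations and handling of pouches.

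**What to change.** In 5.5, delete the monitor's vial enquiry and state that the site monitor receives no vial count, used or in stock, before database lock. Have the pharmacist send re-order requests by the box to clinical supply staff who have no CRF access and no site-monitoring role. The protocol names a group that prints the labels but does not say who ships the vials, so the recipient must be named. In 5.3, remove the block size from the text that sites and monitors see.

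The cost is wording in two sections and re-routing of stock messages. The monitor loses the ability to check stock during the study, so resupply depends on the pharmacist's requests. Sample size, visits and patient procedures are unchanged.

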5.6 Compliance

The study medication will be administered by the investigator or the subinvestigators.

6. PRIOR AND CONCOMITANT ILLNESSES AND TREATMENTS

6.1 Prior and Concomitant Illnesses

Since this study will be performed in severely ill patients requiring mechanical ventilation, concomitant illnesses, postsurgical complications, or multiple trauma are expected in this population and can be among others:

- Deterioration of underlying diseases such as congestive heart failure or pulmonary insufficiency
- Development of acute respiratory distress syndrome (ARDS) due to aspiration, inhalation of chemicals, overdose of narcotics, or sepsis
- Thoracic or multiple trauma
- Complications after visceral, cardiovascular, pulmonary surgery or post transplantation

6.2 Prior and Concomitant Treatments - Antibiotherapy

Any treatment that are given in addition to the study treatment during the study is regarded as a concomitant treatment and must be documented on the appropriate pages of the CRF and in the subject's medical records, with dose adjustments as and if required. It is expected that a broad spectrum of concomitant treatments will need to be administered to treat the basic underlying disease or condition of these patients, to alleviate their symptoms, or to anticipate possible complications.

This may include antibiotics to treat infections, whenever possible selecting however an agent deprived of activity against *P. aeruginosa* or having demonstrated lack of activity against the specific strain isolated in that given patient. It is recommended to select an antibiotic to be used prior to or during the study for intercurrent infections from the table provided below to facilitate the choice of the investigators, to homogenize antibiotic treatment according to type of infections, and to limit interference with *P. aeruginosa* activity; one of these antibiotics should be given preferentially for empiric as well as for definitive therapy unless the clinical indication and/or resistance profile would justify another antibiotherapy.

Type of Infection	Recommended Antibiotics Deprived of Antipseumonal Activity
Vascular line infections	Methicillin, flucloxacillin, vancomycin, teicoplanin, synergid
Abdominal infections	Ceftriaxone +/- metronidazol
Urogenital infections	Ceftriaxone +/- metronidazol Amoxicillin + clavulanic acid +/- metronidazol
Pulmonary infections	Cetriaxone Amoxicillin + clavulanic acid
Central nervous system infections	Ceftriaxone, vancomycin
Skin infections	Penicillin, vancomycin, teicoplanin Amoxicillin + clavulanic acid

The following antibiotics listed in the table below have antipseudomonal activity and should be avoided for therapy unless the specific colonizing strain happens to be resistant or if mandatory during the study for clinical reasons. These same 11 antibiotics will be screened for MIC on bronchotracheal aspirate at study completion for assessing emergence of resistance.

11 Standard Antipseudomonal Antibiotics Not Recommended for Clinical Use* To Be Tested for MIC Pattern	
Carbenicillin	Ceftazidime
Piperacillin	Gentamycin
Piperacillin + tazobactam	Tobramycin
Imipenem	Amikacin
Ciprofloxacin	Meropenem
Cefepime	

* Except if isolated *P. aeruginosa* strain resistant or if medically indicated

Patients on antibiotherapy with activity against pseudomonas prior to study entry will be maintained in the screening phase for 48 hrs, pending results of the antibiogram on the colonized strain. If found to be susceptible to the antibiotic used, the patient will be excluded from the study; if resistant, the patient will be included in the study. Patients already included in the study but requiring an antibiotic with activity against the colonizing *P.aeruginosa* strain will be maintained in the study. Statistical analysis will be performed in these patients as a subgroup and combined with remaining patients only if the pattern of response between treatments is found to be similar to patients treated with no antibiotics or with antibiotics deprived of antipseudomonal activity.

When suspicion of *P.aeruginosa* pneumonia is raised by the clinical situation, a diagnostic procedure must be performed (BAL, PBS) before an antibiotic with antipseudomonal activity can be given empirically. In the case *P.aeruginosa* pneumonia has been diagnosed (Day x) by quantitative culture, dedicated antibiotherapy to treat *P.aeruginosa* infection is recommended and the patient should be taken out of the study at that stage.

Except for other macrolides no treatment is forbidden during the study as reflected in the inclusion/exclusion criteria. Few clinically significant drug interactions are expected to impact on azithromycin clearance, metabolism or distribution and thus concomitant therapy should not influence the clinical outcome of this study. However it is prudent to monitor plasma concentration of concomitant drug which could be increase, thus leading to toxicity, when administering:

- Drugs such as theophyllin, digoxin, ergotamine, dihydroergotamine, or triazolam
- Compounds metabolized by cytochrome P450 system such as carbamazepine, cyclosporine, hexobarbital or phenytoine
- Drugs known to increase QTc wave such as selected H1-antihistaminics
- During therapy with anticoagulants such as warfarin should be monitored regularly by prothrombin time as performed in this study

Dosages of concomitant drugs should be adapted for the best interest of the patient if required for efficacy and/or safety reasons.

7. STUDY PROCEDURES AND SCHEDULE

7.1 Overview of Data Collection

The schedule of data collection is described in the Study Schedule and in Study *Section 7.2. Description of study days*; the methods of data collection and the analysis variables are described in *Section 7.3. methods of data collection* and in the appropriate Appendices. Preparation of clinical supplies is described in *Section 5.4* and in *Appendix C: Preparation of i.v. supplies*. Prior and concomitant therapy as well as antibiotherapy recommended are described in *Section 6.2*

